5. PARTICIPANT ELIGIBILITY, ENROLLMENT AND WITHDRAWAL

5.1. Description of the Population

A total of up to 24 participants, ≥ 18 years of age and diagnosed with PTSD will be enrolled and treated in this Phase I trial. Participants may be men or women and of any race or ethnicity.

In order to qualify to participate, individuals must satisfy all the Inclusion Criteria and none of the Exclusion Criteria.

5.1.1 Inclusion Criteria

1. Individuals ≥ 18 years of age
2. Have a diagnosis of Post-Traumatic Stress Disorder (PTSD) as defined:
 - Meet Diagnostic and Statistical Manual-5th edition (DSM-5) criteria for current PTSD with a duration of 6 months or longer as assessed by a study psychiatrist.
 - Determination of at least one traumatic event as determined by the LEC-5
 - A score of at least 33 on the PCL-5
3. Willing and able to provide signed informed consent which includes compliance with the requirements and restrictions listed in the informed consent form (ICF) and in this protocol.
 - Willingly agreed to provide verbal consent to provide needed pre-screening information, including medical history, concomitant medications, etc., prior to signing the ICF.
4. Be willing to commit to self-administering the study drug, to completing the QoL and PRO instruments, and attending all study visits.
5. Participants must be able to evaluate their average pain on the BPI (Brief Pain Inventory) over the past week.
6. Acceptable renal functioning as determined by no significant prior medical history and results of clinical laboratory evaluations done at Screening and on Day 1 (e.g., eGFR >45 (mL/min/1.73 m²))

7. Acceptable hepatic functioning as determined by no significant prior medical history and results of clinical laboratory evaluations done at Screening and on Day 1 (e.g., liver enzymes ≤ 1.5 x the upper limit of normal, 'ULN')
8. Agree to only use the psilocybin mushroom provided by site staff and not use any other psilocybin (or similar drug) in any form for at least 30 days prior to Study Day 1 and for 30 days following the single-dose study drug treatment.
9. Is willing to wear, sync daily, and charge twice weekly a provisioned health tracking wearable device every day during sleep and daily activity. If the participant already has the same, or compatible device, they can use their own.
10. Agree to not use any psychoactive drugs, partake alcoholic beverages, self-administer ondansetron (or other selective serotonin reuptake inhibitors 'SSRIs', serotonin-norepinephrine reuptake inhibitors, 'SNRIs' and monoamine oxidase inhibitors, 'MAOs'), cannabis, and/or any other non-routine PRN medications within 24 hours of Study Day 1. Exceptions include daily use of caffeine, nicotine, and opioid pain medication
11. Be stable on any pre-study medications and/or psychotherapy regimen prior to study entry. Agree to inform physician(s)/clinician(s) providing current care about your participation in the study (or permit the research site study staff to do so). Agree to report any changes in medication or psychotherapy treatment regimen during the study, to study staff.
12. If female and of childbearing potential, the participant is eligible for the trial only with a negative urine pregnancy test during Screening and on Study Day 1. [If a result is uncertain (e.g., potential false positive), a serum human chorionic gonadotropin (hHCG) test may be performed prior to the administration of the study drug.] Fertile females agree to use a highly effective form of birth control during the 30-day posttreatment period and must confirm that they have no intent to try to become pregnant or any need to breastfeed during this period.
 - Adequate birth control methods include intrauterine device (IUD), injected or implanted hormonal methods, oral hormones plus a barrier contraception, or double barrier contraception. Two forms of contraception are required with any barrier method or oral hormones (i.e., condom and diaphragm, condom or diaphragm and spermicide, oral hormonal contraceptives and spermicide or condom). Not of childbearing potential is defined as permanent sterilization or postmenopausal females.
13. Be proficient in reading and writing in English and able to effectively communicate with site staff.
14. Agree not to participate in any other interventional clinical trials during the study.

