Study Medication Administration

Provided the participant remains eligible, they will undergo a symbolic ceremony in which intentions are set and then be instructed to self-administer the study drug.

- The participant will self-administer, under observation, a whole, dried, ground organic psilocybin mushroom (RTT1121 also called JMF-01) which has been milled and formulated into 3 solid chocolates.
 - A physician will be onsite, or if observing via video conferencing can reach the study site within 10 minutes in case of a medical emergency.

Post-Dose Monitoring and Assessments

Following the self-administration of the single dose of study drug, participants will be instructed to lie down wearing eyeshades and listen to a preselected music playlist via headphones and speakers. Participants will be closely monitored for medical and psychological (including psychosis) adverse effects to ensure their safety and well-being. Participants also will be assessed via clinician rating scales.

In addition to the therapists (and group) support provided, a trained therapy dog also will be available in the dosing room to offer additional support, if requested by the participant.

- Vital signs are to be measured every 30 minutes for at least 8 hours following study drug administration.
 - If vital signs are abnormal at 8 hours, the participant will remain at the study site for continued observation until the measurements return to baseline values, or the Investigator deems that not further monitoring is needed. Vital sign measurements listed below may be considered abnormal; (however, the Investigator may override these values):
 - Blood pressure above 140/90 mmHg
 - Heart rate outside the range of 50-90 beats per minute
 - Respiratory rate
 - Pulse oximetry – SpO2 ratio $< 92\%$
- Blood samples for PK profiling will be collected at the following timepoints
 - 30 minutes (± 2 mins)

CONFIDENTIAL

- 60 minutes (± 5 mins)
- 90 minutes (± 5 mins)
- 120 minutes / 2 hours (± 5 mins)
- 4 hours (± 15 minutes)
- 8 hours (± 15 minutes)
- Manage participant's complaints of pain and administer pain medication as warranted and record the type(s) and amount(s) administered.
- Nearing the 8-hour timepoint, the following clinician rating scales and participant QoL and PRO instruments should be administered and/or completed by the participant, respectively:
 - GAD-7
 - PHQ-9
 - C-SSRS
 - MEQ30-revised
 - CEQ
 - 5D-ACS
 - WCS
 - BPI

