Below is a list of statements. By circling **one number per question**, please indicate how much you agree with each statement as it applies to you since your life changing experience(s) such as losses i.e. death, divorce, physical disability, serious/life limiting illness, traumatic events, or any other life altering experiences. There is no right or wrong answer to these statements. Your response is based on your unique experiences, so it may not reflect responses of others.

	Strongly Disagree	Disagree	Neither Agree or Disagree	Agree	Strongly Agree
25. My friends provide the support I need during difficult times.	1	2	3	4	5
26. I seek more of a connection in my relationships.	1	2	3	4	5
27. I take more time to be in the moment.	1	2	3	4	5
28. My experience with multiple losses has made it hard to be hopeful during difficult times (such as death, divorce, competency, physical disability).	1	2	3	4	5
29. Working through my own grief has brought meaning to my life.	1	2	3	4	5
30. I have a sense of peace in my life.	1	2	3	4	5
31. I have an increased sense of gratitude.	1	2	3	4	5
32. Being surrounded by nature is meaningful.	1	2	3	4	5
33. Creative arts bring peace to my life.	1	2	3	4	5
34. Life challenges interfere with activities that are important to me.	1	2	3	4	5
35. Life challenges raised my desire to be more positive.	1	2	3	4	5

Exhibit 6
Brief Pain Inventory (BPI)

 1903	Date:  /  /  (month) (day) (year)	Study Name: _____
	Subject's Initials : _____	Protocol #: _____
	Study Subject #:    	PI: _____
		Revision: 07/01/05

[figure not shown]
PLEASE USE
BLACK INK PEN

Brief Pain Inventory (Short Form)

1. Throughout our lives, most of us have had pain from time to time (such as minor headaches, sprains, and toothaches). Have you had pain other than these everyday kinds of pain today?

☐ Yes ☐ No

2. On the diagram, shade in the areas where you feel pain. Put an X on the area that hurts the most.

3. Please rate your pain by marking the box beside the number that best describes your pain at its **worst** in the last 24 hours.

☐ 0 ☐ 1 ☐ 2 ☐ 3 ☐ 4 ☐ 5 ☐ 6 ☐ 7 ☐ 8 ☐ 9 ☐ 10
No Pain Pain As Bad As You Can Imagine

4. Please rate your pain by marking the box beside the number that best describes your pain at its **least** in the last 24 hours.

☐ 0 ☐ 1 ☐ 2 ☐ 3 ☐ 4 ☐ 5 ☐ 6 ☐ 7 ☐ 8 ☐ 9 ☐ 10
No Pain Pain As Bad As You Can Imagine

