5. Please rate your pain by marking the box beside the number that best describes your pain on the **average**.

☐ 0 ☐ 1 ☐ 2 ☐ 3 ☐ 4 ☐ 5 ☐ 6 ☐ 7 ☐ 8 ☐ 9 ☐ 10
No Pain Pain As Bad As You Can Imagine

6. Please rate your pain by marking the box beside the number that tells how much pain you have **right now**.

☐ 0 ☐ 1 ☐ 2 ☐ 3 ☐ 4 ☐ 5 ☐ 6 ☐ 7 ☐ 8 ☐ 9 ☐ 10
No Pain Pain As Bad As You Can Imagine

Date:

--	--

 /

--	--

 /

--	--

(month) (day) (year)

Subject's Initials :

Study Subject #:

Study Name: _____

Protocol #:

Pl: _____

Revision: 07/01/05

PLEASE USE
BLACK INK PEN

7. What treatments or medications are you receiving for your pain?

8. In the last 24 hours, how much relief have pain treatments or medications provided? Please mark the box below the percentage that most shows how much relief you have received.

0% 10% 20% 30% 40% 50% 60% 70% 80% 90% 100%

☐ No Relief ☐ Complete Relief

9. Mark the box beside the number that describes how, during the past 24 hours, pain has interfered with your:

A. General Activity

☒ 0 Does Not Interfere
 ☐ 1
 ☐ 2
 ☐ 3
 ☐ 4
 ☐ 5
 ☐ 6
 ☐ 7
 ☐ 8
 ☐ 9
 ☐ 10 Completely Interferes

B. Mood

☐ 0 Does Not Interfere
 ☐ 1
 ☐ 2
 ☐ 3
 ☐ 4
 ☐ 5
 ☐ 6
 ☐ 7
 ☐ 8
 ☐ 9
 ☐ 10 Completely Interferes

C. Walking ability

☐ 0 ☐ 1 ☐ 2 ☐ 3 ☐ 4 ☐ 5 ☐ 6 ☐ 7 ☐ 8 ☐ 9 ☐ 10
Does Not Completely
Interfere Interferes

D. Normal Work (includes both work outside the home and housework)

☐ 0 ☐ 1 ☐ 2 ☐ 3 ☐ 4 ☐ 5 ☐ 6 ☐ 7 ☐ 8 ☐ 9 ☐ 10
Does Not Completely Interferes

E. Relations with other people

☐ 0 ☐ 1 ☐ 2 ☐ 3 ☐ 4 ☐ 5 ☐ 6 ☐ 7 ☐ 8 ☐ 9 ☐ 10
Does Not Completely
Interfere Interferes

F. Sleep

☒ 0 Does Not Interfere ☐ 1 ☐ 2 ☐ 3 ☐ 4 ☐ 5 ☐ 6 ☐ 7 ☐ 8 ☐ 9 ☐ 10 Completely Interferes

G. Enjoyment of life

[illegible]

Exhibit 7

Columbia-Suicide Severity Rating Scale (C-SSRS)

SUICIDAL IDEATION	

Ask questions 1 and 2. If both are negative, proceed to "Suicidal Behavior" section. If the answer to question 2 is "yes", ask questions 3, 4 and 5. If the answer to question 1 and/or 2 is "yes", complete "Intensity of Ideation" section below.
	Since Last Visit

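### At 8 hours after dosing, two thirds of the window of the BPI's 24-hour items is pre-dose; the current-pain item avoids this but needs a pre-dose BPI that Table 2 does not mark

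*Protocol*

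**What the plan says.** **The form.** Exhibit 6 of the Protocol reproduces the BPI Short Form. Its recall periods differ by item:

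- Item 3 asks for the "number that best describes your pain at its worst in the last 24 hours".
- Item 4 asks for the "number that best describes your pain at its least in the last 24 hours".
- Item 5 asks for the "number that best describes your pain on the average", with no period printed.
- Item 6 asks for the "number that tells how much pain you have right now".
- Item 8 asks "In the last 24 hours, how much relief have pain treatments or medications provided".
- Item 9, parts A to G (interference), refers to the past 24 hours.

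**The timing.** Section 7.1.4 (Study Day 1) states "Nearing the 8-hour timepoint, the following clinician rating scales and participant QoL and PRO instruments should be administered", and the list that follows includes the BPI. The same section also lists the BPI among the pre-dose and baseline instruments. Table 2, the detailed Day 1 schedule, marks the BPI only in the 8-hour column, whereas GAD-7, PHQ-9, C-SSRS and POMS are marked both pre-dose and at 8 hours. Table 1 marks the BPI once for Day 1 and does not separate before from after dosing. Section 7.1.5 repeats the BPI on Study Day 2, about 24 hours after dosing.

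**The use.** Section 4.4.3 includes the BPI among the instruments for which mean change from baseline will be calculated. Section 12.5 plans summaries of change by visit.

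**Eligibility.** Inclusion criterion 5 (Section 5.1.1 and the Synopsis) states "Participants must be able to evaluate their average pain on the BPI (Brief Pain Inventory) over the past week".

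**The concern.** A change score is informative about a single dose only if the later answer describes time after the dose. At 8 hours most items on this form describe mainly the time before it, so the reading is pulled toward the baseline answer. The interference items (work, walking, sleep and so on) are especially hard to read: most of their window is the day before, and for the hours after dosing participants are asked to lie down with eyeshades.

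The schedule adds a second difficulty. If sites follow Table 2 rather than the text of Section 7.1.4, there is no BPI from the same day before dosing. The only earlier one is then from Screening, which may be up to 30 days old, or more if the Screening Period is extended. Neither problem can be repaired later: an analysis plan can choose which item to analyse, but it cannot change the period participants answered about or recover a form that was not completed.

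What is at stake is modest. The BPI is exploratory, although Section 2.2 names pain among the PTSD comorbidities that the trial is meant to inform.

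**Working it through.** The Protocol gives no figure of its own here, so there is none to reproduce.

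**Inputs.** Recall window of items 3, 4, 8 and 9: W = 24 h (Exhibit 6). Time of the post-dose form: t = 8 h (Section 7.1.4, Table 2). Day 2 form: t = about 24 h (Section 7.1.5). Period named in inclusion 5: one week = 168 h.

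**Step 1: share of the window before dosing.** Share = (W − t)/W, not below 0.

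- 24-hour items at 8 h: (24 − 8)/24 = 16/24 = 66.7%. For a form completed 15 minutes either side of 8 h: (24 − 7.75)/24 = 67.7% and (24 − 8.25)/24 = 65.6%.
- 24-hour items on Day 2 at 24 h: (24 − 24)/24 = 0%.
- Item 6 at any time: no look-back, so 0%.

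**Step 2: effect on the score at 8 h.**

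- *Answers that average over the window.* If pain is steady before dosing and then differs by d for all 8 hours, the window average moves by d × 8/24 = d/3.
- *Worst pain (item 3)* is a maximum. With accurate recall it cannot fall from the pre-dose answer unless the earlier worst pain was more than 16 h before dosing. Pain after dosing that exceeds the earlier worst registers in full.
- *Least pain (item 4)* is the mirror image. A new low after dosing registers in full, but the answer cannot rise unless the earlier low was more than 16 h before dosing.

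The loss is therefore not the same for every item. Improvement is diluted in averaged answers and hidden in item 3; worsening is diluted in averaged answers and hidden in item 4.

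**Step 3: the same-day pair.** Item 6 at 8 h minus item 6 pre-dose is free of this problem. The pre-dose value exists if Section 7.1.4 is followed and does not exist if Table 2 is followed.

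**Step 4: item 5 (average).** No period is printed, so its pre-dose share depends on how the participant reads it:

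- Read as 24 hours, like items 3 and 4: 66.7% at 8 h and 0% on Day 2.
- Read as one week, like inclusion 5: (168 − 8)/168 = 95.2% at 8 h, (168 − 24)/168 = 85.7% on Day 2, and (168 − 72)/168 = 57.1% on Day 4.

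The same item could thus mean different things to different participants unless one period is stated.

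**The case against.** A reader might infer that the BPI cannot show a change in pain on the dosing day. The documents do not support that: item 6 has no look-back, and the Day 2 form covers the 24 hours after dosing.

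A reader might also infer that monitoring for worsening pain is compromised. It is not. Section 4.1 has participants closely monitored throughout the 8-hour stay, and Section 7.1.4 has pain complaints managed and the medication recorded; neither depends on the BPI. Item 3 would also register pain above its earlier worst.

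A third tempting reading is that the form's period conflicts with inclusion 5 in a way that affects who is enrolled. Inclusion 5 asks only that participants be able to rate their pain. It sets no score, so nobody is admitted or excluded because of the recall period. Nor is it a clash of 24 hours against a week, because average pain is item 5, which prints no period at all.

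The strongest remaining objection is that nothing names the 8-hour BPI as an analysed efficacy timepoint. Section 4.4.3 gives Study Day 7 as its example, and the choice of item and timepoint for an exploratory endpoint can be left to the SAP. That is fair, and it limits the weight of the point. It does not remove it, because the form, its timing and the disagreement between Section 7.1.4 and Table 2 are fixed in the Protocol. It is also true that GAD-7 and PHQ-9, with two-week recall, are given at 8 hours and look back further, but that does not help the BPI reading.

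**Conclusion.** The point holds as a low-cost improvement to an exploratory measure. At 8 hours, 67% of the window of the worst, least, relief and interference items is pre-dose, and a steady post-dose change appears at about one third of its size in an averaged answer. Item 6 and the Day 2 form are unaffected. The one-third figure assumes steady pain before dosing, a change lasting all 8 hours and accurate recall; a shorter-lived change would show less in an averaged answer. The Day 2 figure assumes that the visit takes place about 24 hours after dosing.

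The disagreement between Section 7.1.4 and Table 2 on the pre-dose BPI is a plain inconsistency, and it decides whether the unaffected same-day comparison is available. The mismatch between inclusion 5 and Exhibit 6 is one of wording and has no eligibility effect.

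**What to change.** 1. Mark the BPI in the pre-dose column of Table 2, to agree with Section 7.1.4.
2. Name item 6 at 8 hours minus item 6 pre-dose as the Day 1 pain change score. At 8 hours, either omit the 24-hour items or state that they will not be interpreted.
3. Use the Day 2 form for 24-hour pain after dosing.
4. Reconcile inclusion 5 with Exhibit 6, and state one recall period for item 5 to be used at every visit.

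The cost is wording, one short pre-dose form that the text already asks for, and no full interference score at 8 hours. Item 6 is also a snapshot: it misses pain that comes and goes between the two readings, and it can reflect pain medication given that day. It should therefore be read beside the medication record that Section 7.1.4 already requires.

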5.1.2 Exclusion Criteria

1. Currently uncontrolled hypertension. ($>140/90$ at Screening and $>145/95$ on Study Day 1).
2. History of recent seizure (within 3 months of Study Day 1).
3. History of stroke or transient ischemic attacks.
4. Preexisting history of valvulopathy or pulmonary hypertension.
5. A marked prolongation of QT interval (i.e., $QT \geq 450$ msec) over a series of 3 ECGs performed within 5-6 minutes.

CONFIDENTIAL

6. Currently uncontrolled diabetes ($HbA1c > 8.0\%$).
7. Potential for adverse drug-drug interactions such as the use of centrally-acting serotonergic agents within 24 hours prior to and for 72 hours following study drug administration on Study Day 1.
8. Significant suicide risk defined by (1) suicidal ideation as endorsed on items 4 or 5 on the Columbia Suicidal Severity Rating Scale (C-SSRS) within the last 6 months, at Screening, or at Baseline (Visit 1), or; (2) suicidal behaviors within the last 12 months as assessed by C-SSRS.
9. Patients with severe anxiety and depression measured as following: Participants with scores of 15 & above on Generalized Anxiety Disorder-7 (GAD-7) scale, and/or with scores of 20 & above on Patient Health Questionnaire-9 (PHQ -9).
10. Are pregnant or nursing or are women of childbearing potential who are not practicing a highly effective means of birth control.
11. Have any allergies or contraindication to psilocybin mushrooms.
12. Current users of psilocybin, LSD, DMT, Ayahuasca, Peyote, mescaline, and ketamine over the past 30 days will not qualify for the study unless the use of these agents is stopped for 30 days prior to Study Day 1 and the participant agrees to not use these (or similar) agents for 30 days after Study Day 1.
13. Are not able to attend face-to-face visits at the study site or plan to move out of the area prior to the 3-month LTFU visit.
14. Have any current problem that, in the opinion of the Investigator or Medical Monitor, might interfere with an individual's participation in the study or confound the assessment of safety and/or efficacy of the study drug.

